8. RATIONALE AND BACKGROUND

Background

TachoSil is a surgical patch used during surgeries to assist with stopping bleeding, sealing tissues, and suture support in vascular surgery where standard techniques are insufficient. It is a combination of a collagen matrix made from horse tendons, coated with human fibrinogen and thrombin, and it is directly applied to the wound surface. TachoSil has received regulatory approval in 71 countries and was granted marketing approval by the European Medicines Agency in June 2004. Until June 8, 2023, an estimated 11.6 million patients worldwide have been exposed to TachoSil. Its approved indications in the European Union (EU) for adults include supportive treatment in surgery, improvement of haemostasis, tissue sealing, suture support in vascular surgery when standard techniques are insufficient and sealing of the dura mater to prevent postoperative cerebrospinal leakage following neurological surgery. In 2010, TachoSil was also approved in the United States as an adjunct to haemostasis when standard surgical techniques fail; in 2015, the indication was expanded to include use in children.

As of March 2023, after positive opinion from the European Medicines Agency, TachoSil has been approved in European Union for supportive treatment in surgery, for improvement of haemostasis, to promote tissue sealing and for suture support in vascular surgery in children from 1 month old to 18 years old, where standard techniques are insufficient.

Rationale

Overall, the safety data of TachoSil generally reflect the type of post-operative complications related to the surgical settings in which the trials were conducted and the underlying disease of the patients. Data from the eight controlled clinical studies conducted by the MAH has been pooled into an integrated dataset. In the integrated analyses, 997 patients were treated with TachoSil, and 984 patients were treated with comparator treatment. Due to practical reasons (comparison to standard surgical and standard haemostatic treatment), blinding was not possible in the TachoSil trials. Therefore, the studies were performed as open-label studies [1].

Paediatric use of TachoSil in the United States was accepted based on two studies including paediatric patients undergoing hepatic surgery, TC-2402-040-SP and TC-019-IN. Study TC-2402-040-SP was a pivotal study, which was a basis for the approval of the paediatric indication by FDA in 2015. This was a randomised, open-label, multicentre study that compared the efficacy and safety of TachoSil *versus* Surgicel (standard US-licensed haemostatic agent), for the secondary treatment of local bleeding after hepatic resection in adult (aged 17 years or older) and paediatric (new-born to 16 years) patients. Twenty paediatric subjects were recruited to TachoSil arm. Eight of them were randomised to TachoSil arm and were included in Full Analysis Set (FAS) (compared to 114 adults randomised to TachoSil group). Other 12 were included in paediatric extension part to those receiving TachoSil (no comparator was involved in this extension phase). All 20 patients were included in Safety Analysis Set (SAS).

Primary efficacy endpoint was the intraoperative haemostasis at target bleeding site within 3 minutes of application of allocated trial treatment. In the paediatric FAS, the proportion of subjects who achieved haemostasis within 3 minutes after TachoSil application was 87.5% (95% CI: 47.3 -99.7%). In SAS (all paediatric patients), haemostasis at 3 minutes after TachoSil application was achieved by 17 out of 20 (85.0%) paediatric patients. In adult

PasTel

population, haemostasis at 3 minutes after TachoSil application was achieved in 92 adult patients (80.7%).

Although no statistical comparison for both populations is available, the results in the paediatric population were numerically similar to those in the adult patients and were also consistent with a single-arm paediatric study TC-019-IN, non-randomised and non-comparative, with only descriptive statistics. Therein, 13 out of 16 (81.3%, 95% CI: 61.8-100%) TachoSil-treated children (median age 15 months, range 2 – 147, months) achieved haemostasis at 3 minutes (primary efficacy endpoint).

Table 3 Summary of results from both paediatric populations studied in TC-2402-040-SP and TC-019-IN. Adult population from study TC-2402-040-SP included for comparison, FAS – full analysis set, SAS – safety analysis set, CI – confidence interval.

Proportion of patients achieving haemostasis within 3 minutes from application			
TC-2402-040-SP		TC-019-IN	
Adults (FAS n=114)	Children		Children n=16
	FAS n=8	SAS n=20	
80.7% 95% CI, 72.3 – 87.5	87.5% 95% CI, 47.3 – 99.7	85% 95% CI, 62.1 – 96.8	81.3% 95% CI, 61.8 – 100.0

The applicant furthermore provided a pooled analysis based on the paediatric patients from the above two mentioned studies TC-019-IN and TC-2402-040-SP. A total of 45 paediatric subjects were included in the paediatric study pool: 36 in the TachoSil group (8 randomised and 12 from the extension part from study TC-2402-040-SP, as well as 16 patients enrolled in TC-019-IN) and 9 in the comparator group (from study TC-2402-040-SP, all randomised).

The majority of subjects in both treatment groups experienced TEAEs that were considered mild or moderate in intensity, all of which were considered not related to study treatment. Incidence of severe adverse events was approximately the same across treatment groups and only 20 of 272 total adverse events were considered severe.

SAEs were reported by 17 of 36 subjects in the TachoSil group and 4 of 9 subjects in the Comparator group. No subjects in either treatment group experienced an SAE that was considered related to study treatment.

Events of special interest were presented for the paediatric study pool in comparison to the comparator Surgicel. More thrombotic/embolic events and postoperative bleedings were seen in the TachoSil-group. Tissue adhesions were similar. Immunogenicity testing and viral serology was not performed in paediatric subjects up to 6 months of age, nor for subjects enrolled in the paediatric extension part. Immunogenicity was tested in 2 children treated with TachoSil and 2 children treated with Surgicel. Only 1 paediatric subject had a 1-month follow-up test, which was negative for antibodies.

PasTel

Table 4 Overall Summary of subjects with events of special interests by treatment studies TC-2402-040-SP and TC-019-IN, paediatric population

Medical Category	TachoSil N=36 n (%)	Comparator N=9 n (%)	Total N=45 n (%)
Thrombotic and embolic events	2 (5.6)	0	2 (4.4)
SAEs	2 (5.6)	0	2 (4.4)
Postoperative bleeding at surgical site	16 (44.4)	3 (33.3)	19 (42.2)
SAEs	5 (13.9)	0	5 (11.1)
Immunological events	4 (11.1)	1 (11.1)	5 (11.1)
SAEs	1 (2.8)	0	1 (2.2)
Abscess and other surgical related infections	2 (5.6)	3 (33.3)	5 (11.1)
SAEs	0	1 (11.1)	1 (2.2)
Tissue adhesions	8 (22.2)	2 (22.2)	10 (22.2)
SAEs	4 (11.1)	1 (11.1)	5 (11.1)

Studies in cardiovascular surgery were not performed, since it was considered not feasible, due to anticipated low enrolment and the heterogeneous nature of bleed sites that would be studied. No post-marketing requirements or commitments for clinical purposes, except from routine post-marketing surveillance, were recommended.

Despite the similarity in haemostasis rates between the target (paediatric) and reference (adult) populations, the small sample size of paediatric patients, wide confidence interval, and the absence of statistical comparison were considered insufficient to support the registration of TachoSil for paediatric use in the EU. Thus, an extrapolation approach was used following relevant guidelines, such as the *Reflection paper on the use of extrapolation in the development of medicines for paediatrics* (EMA/189724/2018) [2] and the *Structured guidance on the use of extrapolation* (EMA/CHMP/13622/2022) [3]. During the development of the extrapolation concept, gaps in knowledge regarding the long-term and delayed effects of TachoSil in the paediatric population were identified. However, it was deemed that the missing data could be collected post-approval through a Post-Authorisation Safety Study (PASS) since the currently available data indicate a very low risk of long-term effects in paediatric patients. This assumption is based on the fact that TachoSil has already been used in paediatric patients in the United States since 2015, and in the EU off-label, with no significant safety concerns reported in the Marketing Authorisation Holder's safety database for paediatric patients. Therefore, a PASS was proposed to address the identified gaps and gather additional safety information.

Alternatively, e.g., in case of stronger bleeding, TachoSil may be applied without pre-moistening, while also pressing gently to the wound for 3-5 minutes.

Pressure is applied with moistened gloves or a moist pad. Due to the strong affinity of collagen to blood, TachoSil may also stick to surgical instruments, gloves or adjacent tissues covered with blood. This can be avoided by cleansing surgical instruments, and gloves and adjacent tissues before application. It is important to note that failure to adequately clean adjacent tissues may cause adhesions. After pressing TachoSil to the wound, the glove or the pad must be removed carefully. To avoid TachoSil from being pulled loose it may be held in place at one end, e.g. with a pair of forceps.

9. RESEARCH QUESTIONS AND OBJECTIVES

The study aims to evaluate long-term safety effects of TachoSil application in paediatric population, as well as short-term outcomes in terms of safety of TachoSil in paediatric patients undergoing cardiovascular, hepatic or other solid organs surgery and polytrauma with injuries of blood vessels, parenchymal organs, lungs requiring the use of drugs for local haemostasis, tissue sealing or suture support in vascular surgery where standard techniques are insufficient. These scientific questions are to be addressed in a prospective, multicentre, non-interventional, uncontrolled, observational, post-authorisation cohort study.

The main purpose of this observational study is to collect long-term or delayed safety data on the use of fibrin sealant TachoSil during surgical procedures in paediatric population, and to estimate the frequency of adverse reactions, including the formation of foreign-body granuloma, over a period of time, extending beyond TachoSil exposure, in a paediatric population of subjects who have been exposed to TachoSil. The study also aims to generate new data to confirm short-term safety of TachoSil in paediatric patients.

9.1 PRIMARY OBJECTIVES

1. To evaluate the occurrence of clinically significant local reactions at the site of TachoSil application, as detected through routine imaging (X-ray, ultrasound, CT, MRI) or intraoperative detection or physical examination.

9.2 SECONDARY OBJECTIVES

1. To determine the occurrence of tissue adhesions, as detected through routine imaging (X-ray, ultrasound, CT, MRI) or intraoperative detection or physical examination.
2. To determine the occurrence of AESIs reported during the perioperative period, including:
 - Thrombotic and embolic events.
Postoperative bleeding at surgical site and at the site of application of the investigational medicinal product.
 - Allergic reactions / Immediate hypersensitivity reactions.
 - Other surgical related infections at the site of application of the investigational medicinal product.
3. To determine the occurrence of adverse events related to the use of the study product in the period from the start of surgery up to 36 months post-surgery.

10. RESEARCH METHODS

10.1 STUDY DESIGN

This is a prospective, multicentre, non-interventional, uncontrolled, observational, post-authorization cohort study aimed at investigating the short- and long-term safety of TachoSil application.

The study will enrol patients undergoing cardiovascular, hepatic or other solid organs surgery, as well as those with injuries of blood vessels, parenchymal organs, lungs requiring the use of drugs for local haemostasis, tissue sealing, and suture support in vascular surgery where standard techniques are insufficient and where TachoSil was used as a secondary haemostatic treatment. The cohort will include patients identified by participating investigators (prospective enrolment). Patients who meet specified inclusion/exclusion criteria and their legal representatives will receive comprehensive information about the study orally and in written form, tailored to their understanding. The investigator will obtain their voluntary, personally signed, and dated informed consent before collecting any study-related information.

Short-term safety data, including adverse events (AEs) and adverse events of special interest (AESIs), will be collected prospectively from the time of informed consent signature, during hospital stay, and until hospital discharge. Time to onset (TTO), duration, severity, outcome, treatment and relatedness to TachoSil will be analyzed for reported AEs and AESI.

All enrolled patients will be followed for up to 36 months after surgery to monitor long-term treatment-related events and their clinically significant consequences.

To minimize stress for patients and caregivers associated with the study and the surgical intervention itself, the number and frequency of follow-up visits during the observation period will align with the routine follow-up procedures of the clinical sites.

Primary endpoint:

1. The proportion of subjects experiencing clinically significant local reactions including abscesses, hematoma formation or foreign body granuloma formulation, at the site of TachoSil application from the start of surgery up to 36 months post-surgery, as detected through routine imaging examinations (X-ray, ultrasound, CT, MRI or intraoperative detection or physical examination).

Clinically significant reactions are defined as those that, in the investigator's opinion, require surgical re-intervention (e.g., relaparotomy, re-laparoscopy) and/or medical treatment due to signs and symptoms, as well as an impairment of organ function, which can be attributed to the product, local application changes at the site of product application noted during surgery or limitation or impairment of organ function noted during physical examination, reported by the patient or detected by abnormal imaging findings

Secondary endpoints:

1. The proportion of subjects experiencing clinically significant tissue adhesions detected from the start of surgery up to 36 months post-surgery, as detected through routine imaging tests such as X-ray, ultrasound, computed tomography, magnetic resonance imaging or relaparotomy or intraoperative detection or physical examination.

Clinically significant reactions are defined as those that, in the investigator's opinion, require surgical re-intervention (e.g., relaparotomy, re-laparoscopy) and/or medical treatment due to signs and symptoms, as well as an impairment of organ function, which can be attributed to the product, local application changes at the site of product application noted during surgery or limitation or impairment of organ function noted during physical examination, reported by the patient or detected by abnormal imaging findings.

2. Proportion of subjects experiencing at least one AESI during the perioperative period (from start of surgery until hospital discharge):

- Thrombotic and embolic events
- Postoperative bleeding at surgical site and at the site of application of the investigational medicinal product
- Allergic reactions / Immediate hypersensitivity reactions
- Other surgical related infections at the site of application of the investigational medicinal product

3. Proportion of subjects experiencing at least one AE related to the use of the study product in the period from the start of surgery up to 36 months post-surgery.

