Follow-up phase: The study phase is scheduled to last for up to 36 months following the date of surgery for each enrolled patient. There are six planned follow-up visits: one at 1 month (\pm 15 days) after surgery, another at 3 months (\pm 15 days), a third at 6 months (\pm 15 days), and a fourth, fifth and sixth visits at 12, 24 and 36 months (\pm 30 days) post-surgery, respectively. However, to minimize stress for patients and caregivers associated with the study and the surgical intervention itself, the number and frequency of follow-up visits during the observation period can be align with the routine follow-up procedures of the clinical sites.

The follow-up visits can be conducted in person at the study site if such visits are routinely performed, or they can take the form of telephone interviews with the patient and/or patient

PasTel

legal representative conducted by the Investigator. In both cases eCRF should be completed with all collected and required by Protocol data.

Patients have the right to discontinue their participation in the study at any time and for any reason, whether specified or unspecified.

Furthermore, a patient/legal representative (if applicable) may be withdrawn from the study if the Investigator determines that the patient no longer meets any of the inclusion/exclusion criteria.

Lost-to-follow-up (LTFU)

To ensure the smooth progress of the PasTel study, it is crucial to minimize the occurrence of lost-to-follow-up (LTFU). Loss-to-follow-up refers to patients and/or their legal representative who, at some point during the study, cannot be reached for further follow-up procedures, resulting in an unknown status and the inability to collect important long-term information, including adverse events. On the other hand, "dropout" refers to patients who voluntarily withdraw from the study, with their health status known upon departure.

To minimize lost-to-follow-up, the following follow-up process will be implemented: If a study participant (or their legal representative) does not respond to the initial telephone contact, up to two reminder calls will be made. If there is still no response after three phone calls, the participant will be sent an email or certified letter. The overall objective is to keep the loss-to-follow-up rate below 10 %. Based on the Corza Medical experience and Feasibility analysis, it is anticipated that the final LTFU will be approximately 10 %.

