- Adverse Events of Special Interest evaluation including treatment of AESIs
- Comorbidities and their evaluation for the assessment of adverse events (AEs / AESI)
- Granuloma occurrence and Tissue adhesions and other clinically significant events for the endpoint
- Vital signs (as per each site's standard of care as blood pressure, body temperature, and heart rate), if available
- Laboratory data (as per each site's standard of care such as: blood count, C-reactive protein [CRP], International Normalized Ratio[INR], Activated Partial Thromboplastin Time [APTT]),if available

Follow-up visits will be scheduled at 1, 3, 6, 12, 24 and 36 months post-surgery.

Study premature discontinuation details (any time from surgery till end of the study)

- Reason for premature discontinuation
- If possible, the following information to be collected: Adverse Events, Adverse Events of Special Interest, Comorbidities and their evaluation for the assessment of adverse events (AEs / AESI), Granuloma occurrence and Tissue adhesions and other clinically significant events for the endpoint
- Vital signs (as per each site's standard of care as blood pressure, body temperature, and heart rate), if available
- Laboratory data (as per each site's standard of care such as: blood count, C-reactive protein [CRP], International Normalized Ratio[INR], Activated Partial Thromboplastin Time [APTT]),if available

PasTel

Table 5 PasTel Study data collection schedule

Collected data (if available)	Screening	Surgery	Hospital Discharge Data (collected during perioperative period defined as standard practice discharge from the hospital after the surgery at the site)	Follow-up Visits/Contacts (months ²)						Study premature discontinuation details (any time from surgery till end of the study)
				1	3	6	12	24	36	
				Visit window: +/- 15 days			Visit window: +/- 30 days			
Informed consent	•									
Demographic Data	•									
Inclusion/Exclusion Criteria	•	•								
Underlying disease	•									
Type and date of surgery		•								
Patient's discharge details			•							
Co-morbidities and their evaluation for the assessment of adverse events (AEs / AESI)	•	•	•	•	•	•	•	•	•	
Concomitant medication	•	•	• ¹	•	•	•	•	•	•	
Specific treatments, such as: ECMO (extracorporeal membrane oxygenation), hypothermia , ECC (extracorporeal circulation), MI-ECC (minimized systems for extracorporeal circulation)		•								
TachoSil usage details		•								

PasTel

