10.5 STUDY SIZE

Approx.4 or more, if required, paediatric surgery centres will participate in the PasTel study.

Based on feasibility assessments, approximately 66 patients are expected to qualify for the study and undergo surgery. All patients who undergo surgery will be included in the analysis. An anticipated dropout rate is 10 %.

The recruitment will be conducted until the planned number of patients is reached. All patients available in the study population will be considered for the analysis.

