- Recovering/Resolving: Condition is improving, and patient is expected to recover from the event
- Recovered with sequelae: As a result of the AE, the patient suffered persistent and significant disability/incapacity (e.g., became blind, deaf or paralyzed)
- Not recovered
- Fatal
- Unknown.

Reporting of adverse events

Throughout the conduct of the study, the Principal Investigator and investigators will be responsible for collecting and reporting adverse events to the Sponsor (Corza Medical). They are responsible for the timely identification, documentation, and reporting of all AEs, AESIs and adverse reactions (ARs) observed during the study. The principal investigator will ensure that all investigators are thoroughly trained in these procedures and understand their responsibilities.

The management of the follow-up of AEs and ARs, including reporting to the sponsor, is a critical component of the study. Investigators are required to provide comprehensive follow-up information on each AE and AR, ensuring detailed documentation of the event's evolution, management, and resolution. This information must be communicated to the sponsor promptly as per the reporting timelines outlined in the protocol. All events that met the definition of an AE and will occur in the period from the patient signing the ICF and until the final follow-up visit (at 36 month \pm 30 days) will be recorded. During follow-up phase of the study, at each contact between the study site and the patient (visit or phone), the patient will be asked no leading questions about AEs, e.g., "Have you experienced any problems since our last contact?"

The investigator will record all AEs on the standard AE Form (electronic CRF). The investigator will record only 1 AE per form.

For SAE/s, the SAE Form (electronic CRF or paper SAE Form if eCRF is out of order) will also be completed. The investigator will have to record the diagnosis if available. If no diagnosis is available, the investigator will record each sign and symptom as individual AEs. The investigator will evaluate the seriousness, severity, outcome, and causality of AEs.

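### The primary 36-month proportion depends on imaging, surgery or examination, but the plan allows telephone follow-up at site-routine frequency and lists no variable showing whether a child was assessed

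*Protocol*

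**What the plan says.** Section 10.1 defines the primary endpoint as a proportion of subjects from the start of surgery to 36 months, with reactions counted "as detected through routine imaging examinations (X-ray, ultrasound, CT, MRI or intraoperative detection or physical examination". The definition of clinical significance that follows is wider: it covers re-intervention, medical treatment and impairment of organ function, including impairment "reported by the patient or detected by abnormal imaging findings".

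On follow-up, section 10.2 plans six visits (1, 3, 6, 12, 24 and 36 months), and section 10.3 and Table 5 schedule the same six. Section 10.1, however, says that "the number and frequency of follow-up visits during the observation period will align with the routine follow-up procedures of the clinical sites", and section 10.2 says that "the number and frequency of follow-up visits during the observation period can be align with the routine follow-up procedures of the clinical sites". Section 10.2 allows contacts in person where that is routine, "or they can take the form of telephone interviews with the patient and/or patient" or the legal representative.

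At discharge and at each follow-up contact, section 10.3 lists one endpoint item: "Granuloma occurrence and Tissue adhesions and other clinically significant events for the endpoint". Footnote 4 of Table 5, attached to that item, describes wound location and how the patch was applied. It says nothing about how the outcome was assessed. Neither section 10.3 nor Table 5 lists the contact mode, or imaging or examination of the application site.

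On the denominator, sections 10.2 and 10.5 say "All patients who undergo surgery will be included in the analysis". Section 10.7 uses all enrolled subjects with at least one application. Section 10.2 also expects at least 60 of 66 to be eligible for analysis.

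**The concern.** The endpoint is defined by how a reaction is found, but the follow-up does not assure that anyone looks. A telephone call is not imaging, surgery or physical examination. If number and frequency follow site routine, a 36-month contact is not guaranteed either, and the intensity of looking can differ between the roughly four sites.

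Positive findings can reach the database. Negative ones cannot be interpreted, because a child whose application site was scanned and found normal looks the same as a child whose site was never looked at. This is a matter of what is collected, so no later analysis plan can recover it.

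The study exists to fill a gap in long-term paediatric safety data. If the primary proportion comes out low, the reader could not tell safety from lack of observation.

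**Working it through.** **Inputs from the protocol.** Planned recruitment 66, dropout 10%, at least 60 eligible for analysis (section 10.2). Loss to follow-up of about 10%, defined separately from dropout (section 10.2). TachoSil arm of the paediatric pool: abscess and other surgical infections in 2 of 36, or 5.6% (Table 4). That category is not the primary composite and serves only as an illustrative rate.

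**1. The plan's own figure.** 66 × (1 − 0.10) = 59.4, which agrees with the stated 60 to within one child. Dropout and loss to follow-up are defined as different categories. If both occur at 10%, 66 × 0.80 = 52.8 or 66 × 0.90 × 0.90 = 53.5, so about 53 children would have known 36-month status, not 60.

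**2. Effect of loss on a crude proportion over all operated children.** Let L be the share lost. Under a constant, low hazard with loss spread evenly over 36 months, a lost child is observed for half the period on average, so the crude proportion is multiplied by (1 − L) + L/2 = 1 − L/2. If all loss comes soon after surgery, the factor is 1 − L.

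| Loss | Even: factor | Early: factor | 5.6% reads as |
|---|---|---|---|
| 10% | 0.95 | 0.90 | 5.3% / 5.0% |
| 20% (both categories) | 0.90 | 0.80 | 5.0% / 4.5% |

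If events cluster before discharge, the constant-hazard assumption fails and later loss costs less than this.

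**3. Effect of non-assessment among retained children.** If a share s of events in retained children can be detected, the proportion is multiplied by s. The protocol gives no telephone share and no detection rate. Over an assumed range of s from 1 to 0.5 the relative shortfall runs from 0 to 50%, and nothing in the listed data would place s within that range.

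**4. What zero events would mean.** The exact two-sided 95% upper limit for 0 events is 1 − 0.025^(1/n): 5.4% for n = 66, 6.1% for n = 59 and 6.7% for n = 53. With 7 children of unknown status (66 − 59) the observed proportion is bounded by 0 and 7/66 = 10.6%. With 13 (66 − 53) the bounds are 0 and 13/66 = 19.7%. Doubt about status is therefore wider than the sampling limit quoted for 66.

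**5. Follow-up passages side by side.** Sections 10.2 and 10.3 and Table 5 give six dated contacts with windows. Section 10.1 says number and frequency will follow site routine; section 10.2 says they can. A site whose routine ends at 12 months would satisfy section 10.1 and miss the 24- and 36-month contacts.

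**The case against.** A reader might infer that the plan counts lost or unexamined children as event-free. The protocol does not say so. Section 10.7 names cumulative incidence next to the rate of occurrence for the primary and secondary endpoints, and a 36-month cumulative incidence can censor lost children. Missing data are left to the SAP, which is not shown. The expected 60 eligible of 66 could even suggest that dropouts leave the analysis, although that sits awkwardly beside the statement that all operated patients are included. This objection stands, and the point is therefore a risk, not a stated rule.

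A reader might also infer that telephone contact cannot find the endpoint. That goes too far. Clinical significance includes re-intervention, treatment and patient-reported impairment, all of which a parent can describe. Data are also transcribed from medical records, so a scan or re-operation recorded at the site can reach the eCRF. Section 12 does say that "the patient will be asked no leading questions about AEs", but this concerns adverse events generally; the endpoint item is collected separately at each contact, and where possible at premature discontinuation.

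Finally, routine detection belongs to a non-interventional design, and section 10.9 admits self-report and accuracy that varies with contact mode. Admitting the limitation does not measure it. Censoring at last contact also does nothing for a child who answers the telephone for 36 months and is never examined.

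**Conclusion.** The concern holds as a defect in data collection and in the follow-up wording. The endpoint's detection rule and the permitted follow-up do not match, the passages on contact frequency conflict, and assessment status is not a listed variable.

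The part that can be sized is modest: 10% loss lowers a crude proportion over all operated children by about 5% in relative terms if even under a constant hazard, and by up to 10% if early. Losing 10% in each of the two categories would double this. The part from telephone-only contact cannot be sized from the protocol, so a claim of a large specific bias would rest on invented shares. The direction, if unassessed children are treated as non-events, is downward. Events that lead to re-intervention or treatment are the least likely to be missed, which limits the harm but does not remove it.

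**What to change.** Make three changes, before data collection starts (planned for 3Q 2026).

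1. Add eCRF fields at each contact, filled from records or interview: in person or telephone; application site imaged, examined or re-operated since the last contact (yes/no, date, modality, finding); date of last known status.
2. Reconcile sections 10.1 and 10.2 with section 10.3 and Table 5 so that at least the 12-, 24- and 36-month contacts take place for every child, with telephone allowed.
3. State that the 36-month cumulative incidence already named in section 10.7, censored at last contact, is the primary estimate. Report beside it the crude proportion, the number of children by assessment status, and bounds for children of unknown status.

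Do not make an analysis restricted to imaged or examined children a main result. In routine care symptoms prompt imaging, so that subset can overstate the risk.

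The cost is a few eCRF fields and one table. No imaging or procedures are added, and section 10.4 already provides for site staff to collect data beyond routine.
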